#### POMC Precursor ELISA:

POMC precursor will be performed by ELISA with antibodies provided by [name]. For this assay capture monoclonal antibody is directed against ACTH 10-18 and detection antibody is directed against  $\gamma$ -MSH. Affinity purified human 31K POMC is used for standards. The assay has 100% crossreactivity with 22K pro-ACTH but none with ACTH,  $\alpha$ -MSH or  $\gamma$ -MSH (16,29,30). Assay sensitivity is 7.5 fmol/ml. Normal values for this POMC precursor have been preliminary established by our group (14) and a large-scale normal value study for plasma POMC levels is currently being conducted by [name]. ACTH will be measured by solid phase, two-site sequential chemiluminescent immunometric assay and cortisol by solid-phase, competitive chemiluminescent enzyme immunoassay (Immulite 1000), UFC by Liquid-Chromotography-Tandem Mass Spectrometry and Late night salivary cortisol by Mass Spectrometry. Insulin will be measured by immunofluorometric assay (DPC Immulite). Glucose will be determined by automatic hexokinase method.

#### TUMOR SIZE CALCULATIONS

Pituitary tumors will be classified as microadenoma (<10 mm) or macroadenoma ( $\geq$ 10 mm) and assessed for cavernous sinus invasion (CSI), ICA encasement, and suprasellar and sphenoid extension with MRI. Invasiveness will be defined by Knosp criteria. Tumor volume will be calculated using the formula:  $0.5 \times \text{width} \times \text{length} \times \text{height}$  (mm^3).

---

## 4.2 Sample size and power considerations

Sample size and power calculation was carried out for percentage change in POMC level from baseline to final study visit based on prior data examining percentage changes in plasma ACTH from before to after Pasireotide treatment in patients with Cushing's disease. In two Cushing's disease studies, percentage lowering of ACTH level was on average 20% with a 15% SD in this change (31,32). This change was clinically significant, it was associated with 100% of subjects having at least 25% reduction in pituitary tumor size and significant reductions in mean 24 urine free cortisol levels (31,32). From these data, we also expect POMC levels to be reduced by 20% with Pasireotide LAR therapy of POMC secreting silent corticotroph tumors. If the true difference from baseline to post-Pasireotide LAR therapy represents a 20% fall in POMC level and SD of this difference is 15% we will be able to reject the null hypothesis that the percentage change in POMC level is 0 with power >90% and 10 pairs of Pasireotide LAR treated patients with a significance level 0.05 using a two-sided paired t-test.

## 5.0 Protocol amendments, other changes in study conduct

### 5.1. Protocol amendments

Any change or addition to this protocol requires a written protocol amendment that must be approved by the CUMC IRB.

Amendments significantly affecting the safety of subjects, the scope of the investigation or the scientific quality of the study, require additional approval by the IRB.

Examples of amendments requiring such approval are:

1. an increase above that specified in the protocol in drug dosage or duration of exposure of subjects
2. a significant change in the study design (e.g. addition or deletion of a control group)
3. an increase in the number of invasive procedures to which subjects are exposed
4. addition or deletion of a test procedure for safety monitoring

These requirements for approval should in no way prevent any immediate action from being taken by the Sponsor-Investigator in the interests of preserving the safety of all subjects included in the trial. If an immediate change to the protocol is felt to be necessary by the investigator and is implemented by her for safety reasons the IRB will be informed within 10 working days.

Amendments affecting only administrative aspects of the study do not require formal protocol amendments or IRB approval but the IRB must be kept informed of such administrative changes.

### 5.2. Recording of data and retention of documents

Subject data collected from source documents will be documented in an anonymous fashion and the subject will only be identified by the subject number, and by his/her initials. If, as an exception, it is necessary for safety or regulatory reasons to identify the subject, the Sponsor-Investigator will keep this information confidential.

The Sponsor-Investigator will maintain source documents for each patient in the study, consisting of all demographic and medical information, including laboratory data, electrocardiograms, etc, and keep a copy of the signed informed consent form. All information on study-specific source documents will be traceable to these source documents in the patient's file.

Essential documents, as listed below, will be retained by the Sponsor-Investigator for as long as needed to comply with national and international regulations (generally 2 years). The investigator agrees to adhere to the document retention procedures by signing the protocol. Essential documents include:

1. IRB approvals for the study protocol and all amendments
2. all source documents and laboratory records
3. Study-specific source document copies
4. patients' informed consent forms (with study number and title of trial)
5. any other pertinent study document

### **5.3. Discontinuation of study**

See section 3.3.2, page 14.

### **5.4 Ethics and Good Clinical Practice**

This study must be carried out in compliance with the protocol and designed to ensure adherence to Good Clinical Practice, as described in:

1. ICH Harmonized Tripartite Guidelines for Good Clinical Practice 1996. Directive 91/507/EEC, The Rules Governing Medicinal Products in the European Community.
2. US 21 Code of Federal Regulations dealing with clinical studies (including parts 50 and 56 concerning informed consent and IRB regulations).
3. Declaration of Helsinki, concerning medical research in humans (Recommendations Guiding Physicians in Biomedical Research Involving Human Subjects, Helsinki 1964, amended Tokyo 1975, Venice 1983, Hong Kong 1989, Somerset West 1996).

The investigator agrees, when signing the protocol, to adhere to the instructions and procedures described in it and thereby to adhere to the principles of Good Clinical Practice that it conforms to.

### **5.5 Institutional Review Board**

Before implementing this study, the protocol, the proposed informed consent form and other information to subjects, will be reviewed by a properly constituted Institutional Review Board. A signed and dated statement that the protocol and informed consent have been approved by the IRB will be obtained prior to study initiation. Any amendments to the protocol, other than administrative ones, will be approved by this committee.

### **5.6 Informed consent**

The investigator will explain to each subject (or legally authorized representative) the nature of the study, its purpose, the procedures involved, the expected duration, the potential risks and benefits involved and any discomfort it may entail. Each subject will be informed that participation in the study is voluntary and that he/she may withdraw from the study at any time and that withdrawal of consent will not affect his/her subsequent medical treatment or relationship with the treating physician.

This informed consent will be given by means of a standard written statement, written in non-technical language. The subject will read and consider the statement before signing and dating it, and will be given a copy of the signed document. If the subject cannot read or sign the documents, oral presentation may be made or signature given by the subject's legally appointed representative, if witnessed by a person not involved in the study, mentioning that the patient could not read or sign the documents. No patient can enter the study before his/her informed consent has been obtained.

Treatments and procedures, as described in the informed consent, that will be paid for as part of this study include the study visits, blood and urine testing, ECGs, gallbladder ultrasound and the study medication Pasireotide LAR. This study will not provide or pay for commercially available medication(s) that subjects are taking and that are part of standard of care. Anti-diabetic medications that may be necessary to start because of Pasireotide LAR using during this study will not be paid for by Novartis or as part of this study. Pituitary MRIs conducted during this study are considered standard of care for patients with pituitary tumors and will be billed to subjects insurance. Other treatments or procedures subjects may receive while they are participating in this study participation and that are not identified in the consent form as being paid for by the study, will not be paid for.

### **Declaration of Helsinki**

The investigator will conduct the trial in accordance with the Declaration of Helsinki.

## 7 Appendices

### 7.1 Appendix 1: Medications known to be associated with QT interval prolongation

The following list of drugs is generally recognized to have a possible association with QT prolongation. This list is not considered to be all inclusive and any questions regarding the QT prolongation potential.

The current list of these drugs can be found on:  
<http://www.azcert.org/medical-pros/drug-lists/drug-lists.cfm>

Drugs that are generally accepted by the QTdrugs.org Advisory Board of the Arizona CERT to have a risk of causing torsade de pointes are listed below.

#### Generic Name Class

Bepidil Anti-anginal / heart pain  
Amiodarone Anti-arrhythmic / abnormal heart rhythm  
Azithromycin Antibiotic  
Disopyramide Anti-arrhythmic / abnormal heart rhythm  
Dofetilide Anti-arrhythmic / abnormal heart rhythm  
Ibutilide Anti-arrhythmic / abnormal heart rhythm  
Procainamide Anti-arrhythmic / abnormal heart rhythm  
Quinidine Anti-arrhythmic / abnormal heart rhythm  
Sotalol Anti-arrhythmic / abnormal heart rhythm  
Clarithromycin Antibiotic / bacterial infection  
Sparfloxacin Antibiotic / bacterial infection  
Erythromycin Antibiotic; GI stimulant / bacterial infection; increase GI motility  
Arsenic trioxide Anti-cancer / Leukemia  
Astemizole Antihistamine / Allergic rhinitis  
Terfenadine Antihistamine / Allergic rhinitis  
Pentamidine Anti-infective / pneumocystis pneumonia  
Probucol Antilipemic / Hypercholesterolemia  
Chloroquine Anti-malarial / malaria infection  
Halofantrine Anti-malarial / malaria infection  
Domperidone Anti-nausea / nausea  
Mesoridazine Anti-psychotic / schizophrenia  
Thioridazine Anti-psychotic / schizophrenia  
Haloperidol Anti-psychotic / schizophrenia, agitation  
Pimozide Anti-psychotic / Tourette's tics  
Chlorpromazine Anti-psychotic/ Anti-emetic / schizophrenia/ nausea  
Cisapride GI stimulant / heartburn  
Levomethadyl Opiate agonist / pain control, narcotic dependence  
Methadone Opiate agonist / pain control, narcotic dependence  
Droperidol Sedative; Anti-nausea / anesthesia adjunct, nausea

## **7.2 Appendix 2: Formula to calculate QTcF**

The QTcF will be calculated with the following formula:

$$\text{QTcF} = \text{QTInterval} / (\text{RRInterval})^{1/3}$$

Use the QTInterval and RRInterval provided by the ECG machine.

All calculations should be part of the source documentation in the patients' files.

---

### 7.3 Appendix 3: Lifestyle measures in association with anti-diabetic treatments

#### Lifestyle recommendations from the ADA (ADA 2013)

You have the power to improve and protect your health. With proper nutrition and physical activity and by making good lifestyle choices (like not smoking), you can feel better, stronger, and healthier, and can lower your risk of diseases such as cancer, diabetes, heart disease and stroke.

#### What is a Healthy Weight?

There's an easy way to find out if your current weight puts you at risk for developing serious diseases. Go to [www.diabetes.org/bmi](http://www.diabetes.org/bmi) and take the Body Mass Index (BMI) test. The results will help you decide if you need to be concerned about your weight.

The Better You Eat, the Better You Feel

#### Here are some basic guidelines to help you and your family make healthier food decisions.

- Eat lots of vegetables and fruits.
- Choose whole grain foods over processed grain products. Try brown rice instead of white. Substitute whole wheat bread for white.
- Eat fish 2 – 3 times a week.
- Select leaner cuts of meat like those that end in "loin."
- Remove the skin from chicken and turkey.
- Eat non-fat dairy
- Drink water and calorie-free non-carbonated beverages.
- Use liquid oils for cooking instead of solid fats.
- Cut back on high calorie snacks like chips, cookies, cakes, and regular ice cream. Look for baked chips and reduced calorie snacks. Or have a piece of fruit instead.
- Watch your portion sizes. Even too much "healthy" food can cause weight gain.

Another resource that you might find valuable is the American Diabetes Association's online nutrition tool, My Food Advisor. Here you can find recipes, compare foods, search for healthier alternatives and calculate calories, carbohydrates and other nutrients for a meal, a recipe or a whole day of food.

#### Tips:

- Compare labels of similar foods, then choose the one with smaller amounts of saturated fat, cholesterol and sodium.
- Adults should eat less than 2400 mg. of sodium per day. If you have high blood pressure, you should aim for even less.
- Try adding herbs and spices in your cooking to take the place of salt for enhancing flavor.

To learn more about comparing foods and making healthier choices, go to [www.diabetes.org/myfoodadvisor](http://www.diabetes.org/myfoodadvisor).

#### A Little Physical Activity Goes a Long Way

Anything that gets you up and moving is good for you. Here's what it can do:

- Reduce your risk of developing type 2 diabetes
- Reduce your risk of heart disease and stroke
- Lower blood pressure and cholesterol

- Reduce blood glucose (sugar) levels if you have diabetes, which can reduce your risk of developing diabetes-related complications

- Relieve stress
- Help you lose weight
- Give you more energy
- Help you sleep better
- Build stronger bones and muscles

You don't need to go to a gym, play sports or use fancy equipment. Of course, you should talk to your doctor before starting any exercise regimen.

**If You Have Diabetes**

Eating healthy and staying active are even more important if you have diabetes. Well balanced meals can help keep your glucose (sugar) level as close to normal as possible.

Being active also helps you lower your blood glucose. If you increase your level of physical activity, you may be able to take less insulin or diabetes pills. If you're very inactive, have heart disease or a history of foot ulcers, consult your doctor about safe exercise for you.

Check your blood glucose before exercising. If it's under 100 mg/dl, eat some fruit, crackers or have a glass of milk or juice. Check it again after exercising to learn how your blood sugar responds to exercise.

7.4 Novartis Adverse Event Reporting Forms

EXHIBIT A

**7.5 Appendix 5: Patient Quality of Life Questionnaires****EQ-5D-5L Questionnaire**

Under each heading, please check the ONE box that best describes your health TODAY

**MOBILITY**

- I have no problems walking
- I have slight problems walking
- I have moderate problems walking
- I have severe problems walking
- I am unable to walk

**SELF-CARE**

- I have no problems washing or dressing myself
- I have slight problems washing or dressing myself
- I have moderate problems washing or dressing myself
- I have severe problems washing or dressing myself
- I am unable to wash or dress myself

**USUAL ACTIVITIES** (e.g. work, study, housework, family or leisure activities)

- I have no problems doing my usual activities
- I have slight problems doing my usual activities
- I have moderate problems doing my usual activities
- I have severe problems doing my usual activities
- I am unable to do my usual activities

**PAIN / DISCOMFORT**

- I have no pain or discomfort
- I have slight pain or discomfort
- I have moderate pain or discomfort
- I have severe pain or discomfort
- I have extreme pain or discomfort

[figure not shown]
**ANXIETY / DEPRESSION**

- I am not anxious or depressed
- I am slightly anxious or depressed
- I am moderately anxious or depressed
- I am severely anxious or depressed
- I am extremely anxious or depressed

**We would like to know how good or bad your health is TODAY.**

- This scale is numbered from 0 to 100.
- 100 means the best health you can imagine. means the worst health you can imagine.
- Mark an X on the scale to indicate how your health is TODAY.
- Now, please write the number you marked on the scale in the box

YOUR HEALTH TODAY =

**Cushing's Syndrome Quality Of Life Questionnaire**

The following sentences refer to what you may think or feel about your Cushing's syndrome. Your answers will help us to know how you feel and how much your illness has interfered in your usual activities in **the past 4 weeks**.

Below each sentence you will find several response choices. Please read each sentence carefully. After reading each sentence, check the box next to the answer that best describes what you think is happening to you.

There are NO right or wrong answers. We are simply interested in what is happening to you because of your Cushing's syndrome.

I have trouble sleeping (I wake up during the night; it takes me a long time to get to sleep, etc.).

- Always
- Often
- Sometimes
- Rarely
- Never

I have pain that keeps me from leading a normal life.

- Always
- Often
- Sometimes
- Rarely
- Never

My wounds take a long time to heal.

- Always
- Often
- Sometimes
- Rarely
- Never

I bruise easily.

- Always
- Often
- Sometimes
- Rarely
- Never

I am more irritable, I have sudden mood swings and angry outbursts.

- Always
- Often
- Sometimes
- Rarely
- Never

I have less self-confidence, I feel more insecure.

- Always
- Often
- Sometimes
- Rarely
- Never

I'm worried about the changes in my physical appearance due to my illness.

- Always
- Often
- Sometimes
- Rarely
- Never

I feel less like going out or seeing relatives or friends.

- Always
- Often
- Sometimes
- Rarely
- Never

I have had to give up my social or leisure activities due to my illness.

- Always
- Often
- Sometimes
- Rarely
- Never

My illness affects my everyday activities such as working or studying.

- Always
- Often
- Sometimes
- Rarely
- Never

It's difficult for me to remember things.

- Always
- Often
- Sometimes
- Rarely
- Never

I'm worried about my health in the future.

- Always
- Often
- Sometimes
- Rarely
- Never

**Beck Depression Inventory Questionnaire**

This depression inventory can be self-scored. The scoring scale is at the end of the questionnaire.

1.
  - 0 I do not feel sad.
  - 1 I feel sad
  - 2 I am sad all the time and I can't snap out of it.
  - 3 I am so sad and unhappy that I can't stand it.
2.
  - 0 I am not particularly discouraged about the future.
  - 1 I feel discouraged about the future.
  - 2 I feel I have nothing to look forward to.
  - 3 I feel the future is hopeless and that things cannot improve.
3.
  - 0 I do not feel like a failure.
  - 1 I feel I have failed more than the average person.
  - 2 As I look back on my life, all I can see is a lot of failures.
  - 3 I feel I am a complete failure as a person.
4.
  - 0 I get as much satisfaction out of things as I used to.
  - 1 I don't enjoy things the way I used to.
  - 2 I don't get real satisfaction out of anything anymore.
  - 3 I am dissatisfied or bored with everything.
5.
  - 0 I don't feel particularly guilty
  - 1 I feel guilty a good part of the time.
  - 2 I feel quite guilty most of the time.
  - 3 I feel guilty all of the time.
6.
  - 0 I don't feel I am being punished.
  - 1 I feel I may be punished.
  - 2 I expect to be punished.
  - 3 I feel I am being punished.
7.
  - 0 I don't feel disappointed in myself.
  - 1 I am disappointed in myself.
  - 2 I am disgusted with myself.
  - 3 I hate myself.
8.
  - 0 I don't feel I am any worse than anybody else.
  - 1 I am critical of myself for my weaknesses or mistakes.
  - 2 I blame myself all the time for my faults.
  - 3 I blame myself for everything bad that happens.
9.
  - 0 I don't have any thoughts of killing myself.
  - 1 I have thoughts of killing myself, but I would not carry them out.
  - 2 I would like to kill myself.

- 
- 3 I would kill myself if I had the chance.
- 10.
- 0 I don't cry any more than usual.
- 1 I cry more now than I used to.
- 2 I cry all the time now.
- 3 I used to be able to cry, but now I can't cry even though I want to.
- 11.
- 0 I am no more irritated by things than I ever was.
- 1 I am slightly more irritated now than usual.
- 2 I am quite annoyed or irritated a good deal of the time.
- 3 I feel irritated all the time.
- 12.
- 0 I have not lost interest in other people.
- 1 I am less interested in other people than I used to be.
- 2 I have lost most of my interest in other people.
- 3 I have lost all of my interest in other people.
- 13.
- 0 I make decisions about as well as I ever could.
- 1 I put off making decisions more than I used to.
- 2 I have greater difficulty in making decisions more than I used to.
- 3 I can't make decisions at all anymore.
- 14.
- 0 I don't feel that I look any worse than I used to.
- 1 I am worried that I am looking old or unattractive.
- 2 I feel there are permanent changes in my appearance that make me look unattractive
- 3 I believe that I look ugly.
- 15.
- 0 I can work about as well as before.
- 1 It takes an extra effort to get started at doing something.
- 2 I have to push myself very hard to do anything.
- 3 I can't do any work at all.
- 16.
- 0 I can sleep as well as usual.
- 1 I don't sleep as well as I used to.
- 2 I wake up 1-2 hours earlier than usual and find it hard to get back to sleep.
- 3 I wake up several hours earlier than I used to and cannot get back to sleep.
- 17.
- 0 I don't get more tired than usual.
- 1 I get tired more easily than I used to.
- 2 I get tired from doing almost anything.
- 3 I am too tired to do anything.
- 18.
- 0 My appetite is no worse than usual.
- 1 My appetite is not as good as it used to be.
- 2 My appetite is much worse now.
- 3 I have no appetite at all anymore.
- 19.
- 0 I haven't lost much weight, if any, lately.
- 1 I have lost more than five pounds.

- 
- 2 I have lost more than ten pounds.  
 3 I have lost more than fifteen pounds.
20.  
 0 I am no more worried about my health than usual.  
 1 I am worried about physical problems like aches, pains, upset stomach, or constipation.  
 2 I am very worried about physical problems and it's hard to think of much else.  
 3 I am so worried about my physical problems that I cannot think of anything else.
21.  
 0 I have not noticed any recent change in my interest in sex.  
 1 I am less interested in sex than I used to be.  
 2 I have almost no interest in sex.  
 3 I have lost interest in sex completely.

### INTERPRETING THE BECK DEPRESSION INVENTORY

Now that you have completed the questionnaire, add up the score for each of the twenty-one questions by counting the number to the right of each question you marked. The highest possible total for the whole test would be sixty-three. This would mean you circled number three on all twenty-one questions. Since the lowest possible score for each question is zero, the lowest possible score for the test would be zero. This would mean you circles zero on each question.

You can evaluate your depression according to the Table below.

Total Score	Levels of Depression
1-10	These ups and downs are considered normal
11-16	Mild mood disturbance
17-20	Borderline clinical depression
21-30	Moderate depression
31-40	Severe depression
over 40	Extreme depression

**PERSISTENT SCORE OF 17 OR ABOVE INDICATES THAT YOU MAY NEED MEDICAL TREATMENT. IF YOU HAVE ANY CARDIAC CONCERNS, PLEASE CONTACT CARDIOVASCULAR INTERVENTIONS, P.A. at [contact]**

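### The Beck form's self-scoring bands can label a patient who marks a wish or intent to kill themselves as normal, and item 9 carries no message of its own

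*Combined protocol and SAP*

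**What the plan says.** The form is in section 7.5, Appendix 5. It opens with "This depression inventory can be self-scored. The scoring scale is at the end of the questionnaire". Each of the 21 items is scored 0 to 3. Response 2 of item 9 reads "I would like to kill myself" and response 3 reads "I would kill myself if I had the chance".

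The interpretation page speaks to the patient. It tells them to "add up the score for each of the twenty-one questions by counting the number to the right of each question you marked" and then says "You can evaluate your depression according to the Table below". The table goes by total score alone. A total of 1–10 is labelled "These ups and downs are considered normal" and a total of 11–16 is labelled "Mild mood disturbance". From 17 upwards the labels run from borderline to extreme depression.

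The page ends with its only advice on treatment and its only contact: "PERSISTENT SCORE OF 17 OR ABOVE INDICATES THAT YOU MAY NEED MEDICAL TREATMENT. IF YOU HAVE ANY CARDIAC CONCERNS, PLEASE CONTACT", followed by the name of a cardiovascular practice. Nothing on the form singles out item 9.

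**The concern.** A sum can hide the one answer on this form that matters by itself. Under the printed rule, a patient who has just marked a wish or intent to kill themselves can add up a low total and read that their state is normal or mildly disturbed. Nothing on the page tells them to speak to the study team.

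The rest of the page does not make up for this. The treatment message starts at 17 and is worded for a persistent score, so a single completed form does not clearly meet it. The contact is for heart problems, at a practice that appears nowhere else in the text supplied, which suggests that the sheet was not adapted to this study.

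What is at stake is patient safety. No questionnaire is listed as an objective or endpoint (sections 2.2 and 4.1), so the POMC and tumour-volume analyses are untouched.

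**Working it through.** **Inputs**, all from section 7.5, Appendix 5:

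- 21 items, each scored 0–3, added without weights.
- Bands by total: 1–10 (normal), 11–16 (mild), 17–20 and above (borderline or worse).
- Treatment message: persistent total of 17 or above.
- Item 9: 2 points for a wish to kill oneself, 3 points for being ready to do so given the chance.

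**The form's own figure.** Maximum total = 21 × 3 = 63, as the form states.

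**Band reached for each item 9 answer.** Total = item 9 + sum of the other 20 items. Let S be that sum. The label is normal while S ≤ 10 − item 9. It is mild while S lies between 11 − item 9 and 16 − item 9.

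| Item 9 | Normal if S is at most | Mild if S is | Below 17 if S is at most |
|---|---|---|---|
| 2 | 10 − 2 = 8 | 9 to 14 | 16 − 2 = 14 |
| 3 | 10 − 3 = 7 | 8 to 13 | 16 − 3 = 13 |

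**Average per remaining item.**

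- Normal band: up to 8/20 = 0.40 points (item 9 = 2) or 7/20 = 0.35 points (item 9 = 3).
- Below 17: up to 14/20 = 0.70 points or 13/20 = 0.65 points, on a 0–3 scale.

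**Worked cases with item 9 = 3.**

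- All other items 0: total 3, labelled normal.
- Seven other items at 1: total 3 + 7 = 10, still labelled normal.
- Thirteen other items at 1: total 3 + 13 = 16, labelled mild, with no treatment message.

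Item 9 = 1 is left out of this count, because that response states that the thoughts would not be acted on.

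**The case against.** The strongest reply is that harm depends on text that cannot be seen. The table of contents lists a Visit Schedule (3.4.1), but its text is absent, and the surviving part of the assessment table shows no questionnaire row. We therefore do not know when or where the Beck form is completed, whether staff read it on return, or whether the interpretation page goes out with the items. Contact and consent pages were also removed, and section 5.6 gives subjects a copy of the consent, so they may hold a study contact.

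There is also a general route. Section 3.4.2 collects adverse events however they are found. Section 3.4.3 counts medically significant events that may endanger the subject as serious. Section 3.4.4 has the Sponsor-Investigator review each event on learning of it from any source. Patients are seen at baseline and monthly. The band table grades depression and does not claim to assess suicide risk. Low totals with a high item 9 may be rare.

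Much of this stands as a limit on practical reach. It does not change the label that a self-scoring patient reads, possibly before anyone else sees the form. The adverse-event route works only once staff see or hear the answer. It does not name item 9, and it counts conditions present before treatment only if they worsen or become more frequent, so a long-standing thought reported at baseline might not qualify. By contrast, the hyperglycaemia guidance requires patients to bring their glucose diary to the investigator and sets action thresholds. The special monitoring shown covers QT, liver and glucose only.

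It can also be said that one added line about self-harm would be enough. That line would help, but it would leave the contradictory normal label on the same page.

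**Conclusion.** The concern holds for the form as printed. With item 9 at 2 or 3, the printed rule returns a normal label whenever the other 20 items sum to at most 8 or 7, and no treatment message whenever they sum to at most 14 or 13. This follows from the printed bands and needs no outside assumption.

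The practical reach is uncertain. The documents do not show how many of the 10 patients might answer this way, and staff review described in the missing text cannot be excluded. The form should be changed because the printed message is wrong in a grave situation and the change is cheap. Confidence is medium because of the missing pages; the arithmetic is not in doubt.

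**What to change.** On the patient's copy, keep all 21 items unchanged. Remove the self-scoring line, the adding-up instruction, the band table and the cardiovascular contact. Replace them with one line telling the patient to speak to the study team straight away about any thoughts of self-harm or low mood.

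Existing site staff score each form when it is returned, wherever it was completed, and read item 9 separately from the total. Any non-zero item 9 answer goes promptly to the Sponsor-Investigator's review under section 3.4.4, which decides the clinical response. The non-zero trigger is a judgement, set at the lowest level because a needless referral costs little. Persistent totals of 17 or above go to the same review, so the form's existing advice is not lost.

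The cost is one IRB-approved change to one appendix form (section 5.1) and, as an estimate, a few minutes of existing staff time per returned form in 10 patients; how often the form is given is not shown. The downside is that patients lose the immediate self-interpretation and get the 17-point advice through the investigator instead of from the page. No endpoint or analysis changes.
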